7.3 Notifying the service users' GP

A letter will be sent to the service user's GP to notify them that the service user is taking part in the PAAD Study and that stool samples may be taken. Results from diarrhoeal samples will be sent to the GP and care home from the Microbiology Laboratory in the usual manner.

7.4 Screening logs

An anonymous screening log of all ineligible and eligible but not consented/not approached Service Users will be kept at each centre so that any bias from differential recruitment will be detected. The screening log should be sent to the PAAD Trial Manager when all service users have been approached to join the study and those willing to consent have consented.

8 Study procedures

Before any study related procedures are undertaken, the service user's or service user representative's written informed consent will be obtained. Consent to participate in the main observational study for 12 months and consent for the prevalence sub-study 1 will be taken at initial recruitment of service users. All data forms should be as complete as possible and every effort should be made to collect the data at the desired time points for the appropriate participant.

Table 1 details the PAAD Case Report Form (CRF), time point for data collection and who has overall responsibility for collecting the data. The original CRF will be sent to the PAAD Trial Manager (see contacts for address details) and a copy kept at the care home. The PAAD Study research nurse or NISCHR research nurses/officers, where required, will also able to collect any of the data listed below.

CRF	Time point	Collected by
Eligibility/recruitment CRF	Immediately post consent/assent	Care home staff
Baseline CRF	Immediately post consent/assent	Care home staff /Research Nurse
Prevalence Study Stool CRF	Within one week from consent	Care home staff /Research Nurse
Antibiotic CRF	Day of commencement of antibiotic treatment until duration end date	Care home staff /Research Nurse
Stool Chart CRF	Day of commencement of antibiotic treatment, every day for duration of antibiotic + 8 weeks	Care home staff /Research Nurse
Loose Stool CRF	When participant develops diarrhoea.	Care home staff /Research Nurse
Withdrawal CRF	Following a withdrawal	Care home staff
SAE CRF	Following any adverse event	Care home staff

Table 1 Data collection table

8.1 Body measurements

At baseline, at the time of being prescribed antibiotics and at the end of the eight week follow up, an assessment of body composition/nutrition status (MUST score) will be taken. Where it is not possible to weigh a service home user the Mid Upper Arm Circumference (MUAC) will be done.

8.2 Medication Record

During the collection of Baseline CRF and Antibiotic CRF, a photocopy of the Medication Record from the CARE Home Plan of each consented Service User will be taken either by a member of the Care Home staff registered onto the PAAD study or by one of the Research Officers from the National Institute of Social Health Care Research CRC South East Wales Research Network, (NISCHR, ROs). The photocopy of the medication record will be anonymised by the NISCHR ROs and faxed to the Trial manager at SEWTU. This procedure will be repeated after the service user is prescribed an antibiotic at any time point during the study period.

8.2.1 End of Study Search of Medication Records

At the end of the recruitment period the antibiotics prescribed for each consented service user, as determined from the PAAD Case Record Forms (CRFs), will be checked against the original Medication Records retained with the Care Home Plan for each service user. This data will be collected by Trial Manager, Trial Data Manager, Research Nurses and NISCHR Research Officers. A separate CRF will be designed to transcribe this data.

This procedure will be carried out to determine whether all antibiotics prescribed for service users, recruited at care homes, has been captured as part of the PAAD Observation study.

8.3 Antibiotic CRF and Stool Chart

As soon as the service user has been prescribed an antibiotic, the antibiotic CRF needs to be completed on day 1 and thereafter until the end of the antibiotic course. Every day stools will be assessed based on the Bristol Stool Chart (see Appendix 1) and type noting on the Stool Chart CRF

8.4 Multiple antibiotic prescription during the follow up period

If the service user is advised to stop the antibiotics and then restart or they are given a new prescription of antibiotics within the follow up period, the antibiotic CRF and eight week stool chart should commence again.

8.5 Microbiology and Stool sample collection (baseline prevalence stool and loose stool)

A standardised protocol on when and how to take a stool sample will be provided.

Baseline prevalence stool sample:

The baseline prevalence stool samples will be collected by a care home staff / study research nurse and should be collected within one week of consent. The sample will be put into containers provided by the study team, which are recommended by the Microbiology laboratory. This container will be labelled with the participants ID number, initials and date of birth and sent by 1^{st} Class Royal Mail using Post Office approved SafeboxesTM, a method that meets legal requirements. The sample will be sent to the Public Health Wales Microbiology laboratory for *C. difficile* culture and storage at -70°C. Any cultured *C. diff* isolates will be ribo-typed, toxin tested, and have antimicrobial sensitivity testing done, as well as screening for carriage of antibiotic resistant bacteria. Results on baseline samples are for research purposes only and will not be sent back to care homes or GPs. The research team will receive results of study diagnostic stool sample analyses.

Loose Stool sample:

Diagnostic samples (DS) from service users who develop AAD will be sent, as per routine procedure, to local laboratories for routine analysis to include testing for the presence of *C.difficile* toxins A and B, and results will be sent back to the GP, who will subsequently notify the care home of the result. Another sample will be sent, along with the appropriate stool CRF, to central reference laboratory for *C.difficile* culture as above and as well as screening for carriage of antibiotic resistant bacteria. The results of study diagnostic stool sample analyses will be sent to the SEWTU. Expert guidance and support will be given to the care home staff and the GP on how to manage positive results.

8.6 Withdrawal & loss to follow-up

Participants will be given every encouragement to adhere to protocol procedures and follow-up, in order to reduce biases. However, a participant has the right to withdraw consent for participation in any aspect of the PAAD Study at any time. The participants care will not be affected at any time by declining to participate or withdrawing from the trial.

The care home will inform the PAAD Trial Manager of either death or movement to another facility within eight weeks of being prescribed an antibiotic (the follow up period) for all service users participating in the PAAD Study. Service users will be asked for consent for their care home, primary and secondary health care records (care home and medical records) to be examined and for relevant data to be extracted.

9 Pharmacovigilance

9.1 Definitions

Adverse Event (AE): Any untoward medical occurrence in a study participant.

Serious Adverse Event (SAE): Any untoward and unexpected medical occurrence or effect that:

- Results in death
- Is life-threatening*
- Requires hospitalisation, or prolongation of existing hospitalisation
- Results in persistent/significant disability or incapacity
- Is a congenital abnormality or birth defect
- Is otherwise considered medically significant by the investigator.

*refers to an event during which the participant was at risk of death at the time of the event; it does not refer to an event which might have caused death had it been more severe in nature

Related AE:

The AE resulted from administration of any of the research procedures such as a clinical infection caused by one of the probiotic organisms. (Causal to the research process or intervention)

Unexpected AE:

The event is unexpected and for Sub-study 2; Probiotic feasibility an unexpected event will be any event that is not listed as a known adverse effect.

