2.1.3 C. difficile associated diarrhoea (CDAD)

C. difficile associated diarrhoea (CDAD) is the most commonly identified cause of AAD, and most cases of pseudomembranous colitis. CDAD typically occurs in hospitals (including community hospitals) but also occurs in care homes and primary care settings (DH website). CDAD occurs most often as a consequence of disruption of the indigenous protective colonic microflora following broad-spectrum antibiotic treatment. *C. difficile* accounts for 20-30% of AAD [6], although some estimates are more conservative [7]. In the majority of patients,

full recovery is usual, although particularly elderly and frail patients may suffer loss of dignity, become seriously ill with dehydration as a consequence of the diarrhoea, and may progress to develop life threatening pseudomembranous colitis.

Exposure to antibiotics within the previous 2 months is the most important risk factor for developing CDAD [8]. other well recognised risk factors include age (hospital patients aged over 65 years are four times more likely to develop CDAD compared to younger, general medicine patients: 73.6 vs. 16 per 1000 admissions), hospitalisation, severity of underlying illness, nasogastric tube and use of proton pump inhibitors or H_2 agonists [9-11].

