9.2 Reporting procedures

Reporting responsibilities of the centre:

Where the adverse event meets one of the serious categories an SAE form should be completed by the care home staff allocated responsibility on the delegation of responsibilities log. The SAE form should be faxed to the PAAD study manager within 24 hours upon becoming aware of the event.

[contact]

Evaluating and Reporting:

The designated PAAD clinical assessors will assess the nature of the SAE in Sub study 2: Probiotic feasibility for seriousness, causality and expectedness. The study manager will assess the nature of the SAE in all other cases and refer to clinician if necessary. Following the initial report, follow up data may be requested by the PAAD study Manger. Where the SAE is both related and unexpected the PAAD Trial Manger will notify the main REC within 15 days of receiving notification of the SAE.

10 Study outcomes

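### Section 9.1, section 9.2 and Table 1 set three different triggers for the SAE form, and 9.1 read literally leaves out anticipated serious events

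*Protocol*

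**What the plan says.** The protocol describes when an SAE form is due in three places.

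- **Section 9.1.** An adverse event is "Any untoward medical occurrence in a study participant". A serious adverse event is "Any untoward and unexpected medical occurrence or effect that" meets one of the listed criteria, among them "Requires hospitalisation, or prolongation of existing hospitalisation". The entry for an unexpected event reads "The event is unexpected and for Sub-study 2; Probiotic feasibility an unexpected event will be any event that is not listed as a known adverse" (final word omitted).
- **Section 9.2.** The instruction to centres is: "Where the adverse event meets one of the serious categories an SAE form should be completed by the care home staff" with delegated responsibility. Evaluation follows, and the ethics committee is notified "Where the SAE is both related and unexpected".
- **Section 8, Table 1.** The time point for the SAE CRF is "Following any adverse event".

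Three other sections bear on the point. Section 14.1 has the Chief Investigator or a delegate assess seriousness, causality and expectedness once an SAE has been received. Section 2.1.3 says that elderly and frail patients may "become seriously ill with dehydration as a consequence of the diarrhoea". Section 8.6 requires homes to notify deaths and moves to another facility within eight weeks of an antibiotic prescription, and seeks consent to examine care home and medical records.

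**The concern.** Expectedness normally decides how an SAE is handled once it has been reported. Section 9.1 makes it a condition for being an SAE at all. A serious outcome that the protocol itself anticipates could then be left off the form by someone applying the definition as written.

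Stage 1 is meant to establish how important AAD is in care homes (section 3). Section 11.2 says that duration and severity will be known when Stage 2 is considered. Serious events are informative about severity, and their recorded number would depend on which section a home's staff followed. Stage 1 also pilots trial procedures for Stage 2 and aims to prepare homes for a drug trial (sections 1.1 and 11.2), so a faulty SAE definition could be carried forward.

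**Working it through.** No arithmetic applies: the protocol gives no SAE rate and plans no SAE analysis. The check is to apply each rule, as written, to the same three events.

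| Event | 9.1 definition | 9.2 instruction | Table 1 |
|---|---|---|---|
| Serious and anticipated (e.g. admission for dehydration) | not an SAE | form due | form due |
| Serious and unanticipated | SAE | form due | form due |
| Not serious | not an SAE | no form | form due |

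**The sets are nested.** Section 9.1 gives the smallest set, 9.2 a larger one, and Table 1 the largest. Section 9.2 differs from 9.1 by the anticipated serious events. Table 1 differs from 9.2 by the non-serious events. Any loss therefore comes from 9.1 alone; Table 1 taken literally would over-report.

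**Which wording is out of line.** Section 9.2 sends on to the ethics committee those SAEs that are both related and unexpected, and 14.1 assesses expectedness after receipt. If every SAE were unexpected by definition, neither expectedness check would have anything to do. The protocol's own reporting scheme works only if the SAE definition carries no expectedness condition.

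**Whether the condition can be applied.** The entry for an unexpected event is circular for the main study: it says that the event is unexpected. The only reference standard, a list of known adverse effects, is tied to the probiotic feasibility Sub-study 2. Section 17.2 replaces that sub-study with a qualitative observation of care routines. Nothing remains against which staff could judge a main-study event. Given section 2.1.3, they could reasonably regard serious dehydration as expected.

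**After the correction.** With the condition removed from 9.1 and Table 1 limited to serious events, all three columns read: form due, form due, no form. This is the set that 9.2 already requires.

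**The case against.** The best defence is that 9.2 is the operative instruction. It addresses the centres, it refers to adverse events (which carry no expectedness condition), and hospitalisation is a listed category. An admission for dehydration triggers a form under 9.2 and under Table 1; only the opening words of the 9.1 definition lose it. The Table 1 row is labelled as the SAE CRF, so its time point may be shorthand. This defence stands as far as it goes: it makes the loss possible, not certain. It does not remove the contradiction, because 9.1 is where a reader looks up what an SAE is.

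Three stronger readings are tempting, and the documents do not support them.

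- *Many deaths would go unrecorded.* A reader might apply an annual mortality to the 270 residents. The protocol gives no mortality figure, many of those residents would never receive an antibiotic (11.1 estimates that 40% are prescribed one over 12 months), and 8.6 notifies deaths within eight weeks of a prescription by a separate route.
- *Hospital admissions are known only through the SAE form.* Section 8.6 allows records to be examined and data extracted, and a move to another facility might be taken to include hospital. What can be said is that, of the prospective reporting routes, the SAE definition is the one that names hospitalisation.
- *Care home staff are assigned the expectedness judgement.* No section gives them that task; 14.1 places it after receipt. It falls to them only as a consequence of reading 9.1 literally.

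It is also fair to say that SAE counts are neither a listed measure in section 10.1 nor a planned analysis in 12.1.

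**Conclusion.** The contradiction is real. Sections 9.1 and 9.2 and Table 1 prescribe three different reporting sets, and the expectedness condition in 9.1 conflicts with the scheme in 9.2 and 14.1. The consequence is limited. Anticipated serious events may be missed where a home follows 9.1, and the effect falls mainly on serious non-fatal events, since 8.6 covers deaths and transfers in the eight weeks after a prescription. The AAD incidence estimate and the sample size are unaffected. How many events are involved cannot be stated from the protocol.

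The conclusion assumes that some staff would apply 9.1 as worded and would take the description in 2.1.3 as making serious dehydration expected. If every home worked from 9.2, nothing serious would be lost. The correction is worth making because it is cheap and changes which serious events the text requires to be reported.

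**What to change.** Make two edits:

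1. In the SAE definition of section 9.1, delete the words *and unexpected*, so that expectedness is judged only after the report, as 9.2 and 14.1 provide.
2. In Table 1, change the SAE CRF time point to *Following any serious adverse event*.

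The cost is two wording changes and some additional SAE forms compared with a literal reading of 9.1. Compared with 9.2 as it stands, no extra forms are required.

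These edits do not repair the circular entry for an unexpected event, which would then matter only for ethics committee notification. They also leave a mismatch over who assesses main-study SAEs: the study manager in 9.2, and the Chief Investigator or a delegate in 14.1. Both should be reconciled at the same time.

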9.2 Reporting procedures

Reporting responsibilities of the centre:

Where the adverse event meets one of the serious categories an SAE form should be completed by the care home staff allocated responsibility on the delegation of responsibilities log. The SAE form should be faxed to the PAAD study manager within 24 hours upon becoming aware of the event.

[contact]

Evaluating and Reporting:

The designated PAAD clinical assessors will assess the nature of the SAE in Sub study 2: Probiotic feasibility for seriousness, causality and expectedness. The study manager will assess the nature of the SAE in all other cases and refer to clinician if necessary. Following the initial report, follow up data may be requested by the PAAD study Manger. Where the SAE is both related and unexpected the PAAD Trial Manger will notify the main REC within 15 days of receiving notification of the SAE.

10 Study outcomes

10.1 Measures/assessment instruments

Domain	Measure	Collection
		Method
Sample size calculation	 Antibiotic prescribing: what, why, dose, route, frequency, duration Number of AAD & CDAD AAD & CDAD Outcome (MUAC/MUST) C. difficile asymptomatic carriage 	CRF
Piloting Procedures	 Recruitment and consent Testing data collections tools Acceptability of giving probiotic, QoL completion 	CRF Qualitative interview
Develop training materials	1. Training materials	Feedback sessions
Incidence	 AAD CDAD 	CRF

11 Statistical considerations

11.1 Sampling frame and sample size

We will recruit care homes (residential & nursing) within South East Wales. This will be a purposive sample, in that it will ensure contrasting care homes are recruited to include residential, nursing and dual care. The sampling frame will be based on the following criteria:

1) Predominant type of care - residential/nursing/dual

Care homes will be split into three strata, based on the type of care home: nursing, residential and dual. Three from each care homes from each stratum will be recruited to total nine care homes. Recruiting three randomly selected care homes from each of the different strata will allow some insight into the amount of variability between and within different types of care homes (both in terms of the homes themselves and their residents).

Nine care homes will give a sample of approximately 270 Service users. From previous literature, we estimate 40% of care home users are likely to be prescribed antibiotics over a 12 month period. This will enable us to fit a 95% confidence interval to an AAD rate of 25% of +/- 10%. One family focus group around the issues of consent and assent will be conducted in each care home. Additional interviews will be conducted with study participants capable of consent.

11.2 Timing and criteria to justify Stage 2

We will evaluate three months of data collection regarding antibiotic use in nine care homes, together with two additional months of data for AAD. This analysis will provide us with numbers of asymptomatic carriers of *C.diff*, and provide an estimate of numbers of antibiotic prescriptions and AAD including CDAD. The duration and severity of the AAD will also be known.

This data, along with participant consent and follow-up rates, will be used to justify proceeding to a randomised trial in this setting (i.e. Stage 2).

Feasibility components of Stage 1

The feasibility components of Stage 1 are designed to: Optimise procedures for setting up care homes sites to be able to undertake a clinical trial of an Investigational Medicinal Product (CTIMP); Optimise informed consent process in a vulnerable population;

Estimate rate of agreement to participate;

Optimise rate of sampling for follow-up.

To identify the minimum level of cognitive competence below which EQ-5D data should be collected by proxy.

If we find that these feasibility components are not met and we identify insurmountable obstacles (e.g. inability to adhere to regulatory requirements within a care home setting), our conclusion would be that more infrastructure and set up work will be needed before such a study can be conducted in this setting.

12 Analysis

12.1 Main analysis

The primary objectives for the main observational study are:

1. To fit a 95% confidence interval around the estimate annual AAD rate which we currently estimate to be 25% based on available evidence.

The secondary objectives for the main observational study are;

1. To describe the type, dose and treatment regimes of the antibiotics taken by service users. We will tabulate each type of antibiotic against the frequency and severity of AAD;

2. To tabulate summary statistics of the incidence of *C. difficile*, the number of repeat cases of diarrhoea, duration from onset and severity.

12.2 Sub-Study analysis

Sub-Study 1. Prevalence:

1. To determine the prevalence of asymptomatic carriage of *C. difficile*.

Sub-Study 2. Qualitative Observational Study of Care Home Routines :

Data gathered on the observation schedule will be collated, entered onto a spreadsheet for ease of comparison, and discussed between the 3 observers. Any inconsistencies will be debated and, if necessary, resolved by a further visit. A short report on the daily care routines will be prepared for each home and sent to the matron for validation. Feedback from this validation process will be incorporated into a final report on the daily care routines of the PAAD care homes which will then be used to inform the design of PAAD stage 2.

Sub-Study 3. Qualitative sub study

Data will be analysed using Framework Analysis. This approach involves the following steps: familiarisation, creating a thematic framework, indexing, charting, mapping and interpretation. The thematic framework will be developed iteratively, informed by the data and agreed during study team meetings. NVivo 8 software will be used for the indexing stage. A proportion (20%) of transcripts will be double coded by more than one researcher. Disagreements about coding will be resolved, where necessary, in a series of study group meetings.

Sub-Study 4. EQ-5D Sub Study

Given the relatively small sample and the exploratory nature of this sub-study, the results will be used to generate hypotheses rather than test them. Agreement in overall EQ-5D scores between proxies and the SU will be assessed using the Bland/Altman method to estimate 95% limits of agreement.

As data on the individual EQ-5D dimensions are trichotomous (score = 1, 2 or 3) we will use a Kappa statistic to examine agreement between scores obtained from a relative and carer for both SU/proxy on each dimension.

We will also use a Kappa statistic to examine agreement between the carer, research nurse and SU's assessment of the SUs cognitive ability on the day and, via ANOVA, will explore differences between the average MMSE scores and those who said 'yes' or 'no' regarding the SU's level of cognitive ability.

While disagreement between responses by any subject and his/her proxies can clearly be due to factors other than cognitive impairment, it is still anticipated that on average, the level of agreement in each of the above analyses will get closer to the level of agreement for a 'clearly cognitively competent' sub-group alone. These results will allow exploration of the MMSE score below which EQ-5D data should be collected by proxy in the RCT.

13 Study closure

Trial centres will be notified not to collect any further data post the participant closest to the 12 month data collection period month. The study end date is deemed to be the date of last data capture.

14 Regulatory issues

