17.4.2 Sub Study Objectives

This exploratory sub-study is concerned with the hypothesis that there is an inverse relationship between agreement between SU and proxy EQ-5D scores and the SU's level of cognitive competence. If results support this hypothesis, then a minimum level of cognitive competence will be identified below which EQ-5D data should be administered by proxy. The study will also explore whether a

combination of professional and frequent visitor proxies would be preferable to either proxy alone.

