17.4.6 Analysis

Given the relatively small sample and the exploratory nature of this sub-study, the results will be used to generate hypotheses rather than test them.

Agreement in overall EQ-5D scores between proxies and the SU will be assessed using the Bland/Altman method to estimate 95% limits of agreement.

As data on the individual EQ-5D dimensions are trichotomous (score = 1, 2 or 3) we will use a Kappa statistic to examine agreement between scores obtained from a relative and carer for both SU/proxy on each dimension.

We will also use a Kappa statistic to examine agreement between the carer, research nurse and SU's assessment of the SUs cognitive ability on the day and, via ANOVA, will explore differences between the average MMSE scores and those who said 'yes' or 'no' regarding the SU's level of cognitive ability.

While disagreement between responses by any subject and his/her proxies can clearly be due to factors other than cognitive impairment, it is still anticipated that on average, the level of agreement in each of the above analyses will get closer to the level of agreement for a 'clearly cognitively competent' sub-group alone. These results will allow exploration of the MMSE score below which EQ-5D data should be collected by proxy in the RCT.

Ethics approval

This sub-study is classified as a substantial amendment to the main PAAD study.

18 References

- 1. Havenaar, R.H.I.t., Veld JHS, *Probiotics: a general view.* The Lactic Acid Bacteria in Health and Disease, 1992: p. 1 200.
- Surawicz, C.M., Probiotics, antibiotic-associated diarrhoea and Clostridium difficile diarrhoea in humans. Best Practice & Research Clinical Gastroenterology, 2003. 17(5): p. 775-783.
- 3. Parkes, G.C., J.D. Sanderson, and K. Whelan, *The mechanisms and efficacy of probiotics in the prevention of Clostridium difficile-associated diarrhoea.* Lancet Infect Dis, 2009. **9**(4): p. 237-44.
- 4. Fletcher, K.R. and M. Cinalli, *Identification, Optimal Management, and Infection Control Measures for Clostridium difficile-Associated Disease in Long-Term Care.* Geriatric Nursing, 2007. **28**(3): p. 171-181.
- 5. Monaghan, T., T. Boswell, and Y.R. Mahida, *Recent advances in Clostridium difficile-associated disease.* Gut, 2008. **57**(6): p. 850-860.
- 6. Nelson, R., *Antibiotic treatment for clostridium difficile-associated diarrhea in adults (Review).* The Cochrane Collaboration, 2007(3).

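### Sub-study 4: a fall in resident–proxy EQ-5D agreement does not show which reporter became unreliable, and no planned analysis shows that the proxy is the better one below an MMSE cut-off

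*Protocol*

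**What the plan says.** All references are to the protocol. The visitor is the resident's most frequent visitor, called the relative in sections 12.2 and 14.1.

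- **Objective.** Sections 3.2 and 17.4.2 state a hypothesis linking resident–proxy agreement to the resident's cognitive competence. If it is supported, "a minimum level of cognitive competence will be identified below which EQ-5D data should be administered by proxy". Section 11.2 lists identifying this level among the Stage 1 feasibility components.
- **Overall score.** "Agreement in overall EQ-5D scores between proxies and the SU will be assessed using the Bland/Altman method to estimate 95% limits of agreement" (17.4.6, also 12.2).
- **Dimensions.** A kappa is planned for "agreement between scores obtained from a relative and carer for both SU/proxy on each dimension" (12.2, also 17.4.6).
- **Resident's ability.** A second kappa covers "agreement between the carer, research nurse and SU's assessment of the SUs cognitive ability on the day", and an ANOVA explores "differences between the average MMSE scores and those who said 'yes' or 'no' regarding the SU's level of cognitive ability".
- **Interpretation.** Section 12.2 grants that "While disagreement between responses by any subject and his/her proxies can clearly be due to factors other than cognitive impairment". It then anticipates that agreement in each analysis "will get closer to the level of agreement for a 'clearly cognitively competent' sub-group alone", and concludes: "These results will allow exploration of the MMSE score below which EQ-5D data should be collected by proxy in the RCT".
- **Status.** Sections 12.2 and 17.4.6 call the results hypothesis-generating.
- **Triads.** Section 17.4.3.2 approaches the visitor of any resident entered by consent or assent. Section 14.1 introduces the same step as applying where the resident cannot give informed consent.

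**The concern.** The cut-off is meant to settle whose report Stage 2 should use for residents with low MMSE. That is a comparison of two reporters. Resident–proxy agreement depends on the errors of both and so cannot rank them. It falls if the resident can no longer judge his or her own health. It also falls if the resident's report is sound but the proxy can no longer read a less communicative person.

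The ability kappa and the MMSE ANOVA add information, but only on whether the resident seems able to answer. None of the listed results is set up to show that the proxy's report is better. The protocol's own background (17.4.1) makes proxy error a live possibility: it reports that proxy reliability varies with the type of proxy and with the EQ-5D dimension.

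Section 17.4.1 also says that Stage 2 will use EQ-5D in its economic evaluation and that most subjects are expected to have some cognitive impairment. A misplaced cut-off could therefore move many residents to a worse reporter.

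**Working it through.** The protocol gives no SD, power or computed sample size for this sub-study, so there is no figure to reproduce. The check is structural. Every error size below is an assumption.

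**1. Limits of agreement, overall score.** Let the resident's error SD be s_R and each proxy's be s_P. Errors are taken as independent of each other, and the two proxies' errors have correlation ρ.

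- Resident–proxy half-width = 1.96 × √(s_R² + s_P²)
- Carer–visitor half-width = 1.96 × √(2 s_P² (1 − ρ))

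| Case | s_R | s_P | ρ | Resident–proxy | Carer–visitor | Proxy / resident error variance |
|---|---|---|---|---|---|---|
| Baseline | 0.10 | 0.10 | 0 | 0.277 | 0.277 | 1.00 |
| Resident poor | 0.25 | 0.10 | 0 | 0.528 | 0.277 | 0.16 |
| Proxies poor | 0.10 | 0.25 | 0 | 0.528 | 0.693 | 6.25 |
| Proxies poor, partly shared error | 0.10 | 0.25 | 0.5 | 0.528 | 0.490 | 6.25 |
| Proxies poor, mostly shared error | 0.10 | 0.25 | 0.9 | 0.528 | 0.219 | 6.25 |

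In both single-fault cases the resident–proxy figure is 1.96 × √(0.0100 + 0.0625) = 0.528. The match follows from the symmetry of the formula and does not depend on the values chosen. For a poor-reporter SD from 0.15 to 0.30, with the other at 0.10, the half-width runs from 0.353 to 0.620 whichever party is poor. When the proxy is the poor reporter, its error variance is then 2.25 to 9.0 times the resident's.

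**2. Kappa, three-level dimension.** Suppose each reporter answers at random with probability e, drawing from the same category frequencies as the true states, and is otherwise correct. Then kappa for a pair is (1 − e₁)(1 − e₂).

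- Baseline, all e = 0.1: 0.9 × 0.9 = 0.81
- Resident poor (e = 0.5): resident–carer 0.5 × 0.9 = 0.45; carer–visitor 0.9 × 0.9 = 0.81
- Both proxies poor (e = 0.5): resident–carer 0.9 × 0.5 = 0.45; carer–visitor 0.5 × 0.5 = 0.25

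Again the resident–proxy statistic is identical in the two cases, and only the carer–visitor statistic differs.

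**3. What the third pairing gives.** With three reporters, the resident's error variance can be estimated as (D_resident–carer + D_resident–visitor − D_carer–visitor)/2, where D is the variance of the difference. For ρ = 0 this recovers a resident SD of 0.250 when the resident is poor and 0.100 when the proxies are poor. Simulation (4,000 runs per case, SDs 0.25 and 0.10, ρ = 0) gives how often the worse reporter is correctly identified in the lowest third of MMSE:

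| Triads in that third | Resident is worse | Proxies are worse |
|---|---|---|
| 5 | 92% | 78% |
| 15 | 99.6% | 93% |
| 25 | 99.9% | 98% |

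These counts correspond to triads for 10%, 30% and 50% of about 150 residents (17.4.3). The protocol does not state the share.

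**4. Where it fails.** At ρ = 0.9 the carer–visitor half-width is 0.219, narrower than baseline. The resident SD is estimated as √((0.0725 + 0.0725 − 0.0125)/2) = 0.257 although the true value is 0.10. A sound resident would be taken for the poor reporter.

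**The case against.** **The cut-off does not rest on agreement alone.** A reader might infer that it does. Section 12.2 draws on all the listed results, including the ability kappa and the MMSE ANOVA, and section 17.4.4.1 adds the researcher's own judgement of the resident's ability to complete EQ-5D. This stands. What remains is that all of these describe the resident and none tests the proxy.

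**A carer–relative comparison may already be planned.** Read literally, the dimension kappa is between relative and carer. The wording is ambiguous, so it cannot be said that the comparison is absent. It is not planned for the overall score, and the text does not use it as a control: every analysis is simply expected to move the same way.

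**No rule is fixed.** Sections 12.2 and 17.4.6 speak of generating hypotheses and of exploration, and this protocol covers Stage 1 only. It would go too far to say that the plan contains a decision rule that replaces sound self-reports. Even so, 3.2 and 17.4.2 say that a level will be identified if the hypothesis is supported.

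**Agreement suits one of the stated questions.** Section 17.4.1 asks which proxy better reflects residents' own assessment. For that question, resident–proxy agreement is the natural measure. It does not suit the question of when the resident's report should be set aside.

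**Carer and visitor may share an error.** Both face the same less communicative resident. Step 4 of the working shows that the added comparison then misleads. This objection stands and limits what the fix can claim.

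**Extra pairings are analysis-plan detail.** That has force for plots and layouts. The step from falling agreement to a proxy cut-off is set out in the protocol itself, with its weakness admitted.

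**Conclusion.** The point holds in a limited form. Resident–proxy agreement, overall or by dimension, cannot show which party has become unreliable, and no other listed analysis shows that the proxy is the better reporter. With assumed SDs of 0.10 and 0.25, one and the same half-width of 0.528 covers situations in which moving to the proxy divides the error variance by 6.25 or multiplies it by 6.25. The symmetry is algebra under independent random errors; the sizes are illustrative. A systematic shift would change the mean difference but would still not show who is wrong.

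A reader might also infer that the triads already supply the missing control. The documents do not support this. Under section 17.4.3.2 triads can arise across the range of competence. Under section 14.1 they arise only where the resident cannot consent, which leaves little or no competent reference group. The number of triads is not stated, and stable carer–visitor agreement does not prove proxy accuracy.

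This is a low-cost improvement to an exploratory sub-study whose result is meant to inform Stage 2.

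**What to change.** In sections 12.2 and 17.4.6:

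1. State which pairs the dimension kappa compares, and include carer versus relative explicitly.
2. For triads, report resident–carer, resident–visitor and carer–visitor agreement side by side against MMSE. Include the overall score, and compare the two proxies on the same EQ-5D proxy version.
3. Treat a fall in resident–proxy agreement as support for a proxy cut-off only alongside stable carer–visitor agreement and the researcher's judgement of ability. Where both kinds of agreement fall, report that proxies are not shown to be better. State that stable carer–visitor agreement is not proof of accuracy, because the two may share an error.

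In sections 14.1 and 17.4.3.2:

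4. Reconcile whose visitor is approached. Triads among competent residents are needed as the reference.

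Items 1 to 3 change analysis wording only and need no new instrument. Item 4 is also wording if 17.4.3.2 is what was intended; if 14.1 was followed, visitors of consenting residents would have to be approached as well. The downside is that the comparison rests on the triad subset, which may be small. It is also limited to residents with an MMSE score, which section 17.4.4.1 asks of those able to answer the EQ-5D+C.
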